# *Note: The following part of the procedure is described for a right-handed surgeon.*

**Step 10:** The surgeon uses their left hand to lift the subcutaneous tissues to the left of the 10 mm incision and uses a pair of disposable sterile forceps in their right hand to break through into the subcutaneous tissues that they have exposed with their left hand. The procedure is then repeated with the opposite hands when inserting the same forceps into the subcutaneous tissue on the participant's right side of the abdomen.

Pick up the applicator device and remove the applicators cover on the front of the instrument, ensuring that the syringe applicator is held correctly (Figure 7.3). Do not open the back end of the device as there is a risk of tablets escaping if this is opened prematurely.

[figure not shown]

Figure 7.3: Correct holding of syringe applicator

## *Note: The following description applies to a right-handed surgeon inserting the first implant into the participant's left side of the abdomen.*

**Step 11:** The surgeon uses their left hand to lift the subcutaneous tissues of the abdominal wall just 1-2cm to the left of the incision. The bevel of the applicator should be facing upwards and the applicator is inserted carefully into the incision, ensuring that the applicator is placed under the adipose tissue but above the muscle sheath (Figure 7.4) until firm resistance from the subcutaneous tissues is felt.

[figure not shown]

Figure 7.4: Syringe applicator insertion

**Step 12:** Using the surgeons left hand it is then possible to push the subcutaneous tissues against the applicator until the applicator advances for 5-10 mm. The surgeon's left hand is then moved 5-10 mm away from the incision and lifts up the adjacent subcutaneous tissues. The procedure of then pushing the subcutaneous tissues firmly against the bevel of the applicator will allow another 10 mm of movement along the marked central line. This procedure is repeated a series of times until the applicator is fully inserted and sitting just above the sheath with a significant covering of subcutaneous tissues above the applicator. The applicator's trocar can then be picked up in the surgeon's right hand and the opening of the applicator's rear cap can then occur providing the participant is leaning a little to the left so that there is no risk of tablets being lost from the applicator. The trocar is then inserted firmly (Figure 7.5) so that the tablets are slowly pushed forward while the applicator is slowly withdrawn.

[figure not shown]

Figure 7.5: Insertion of OLANI using Syringe plunger

If this is carried out carefully then tablets will be in a line rather than pushed into one ball (Figure 7.6). It is preferable that the tablets be pushed gently in a line to ensure correct placement.

[figure not shown]

Figure 7.6: Correct positioning of OLANI

**Step 13:** The procedure is then repeated through the same incision using a second applicator syringe to position the OLANI tablets on the other side of the abdomen. The site of each OLANI's will be recorded on the CRF.

#### Step 14: Closure of the incision

It is important that closure be carried out in two layers. The first involves closure of the subcutaneous tissues. This should usually be carried with an absorbable suture. We recommend a 3-0 monocryl or biosyn deep dermal suture layer. The second layer of closure requires the skin to be closed using a cyanoacrylate medical glue. In the practical care of those with addictions the glue has proved to be very acceptable as

participants who fail to return for routine assessment following their procedures do not have the risk of a stitch abscess. Following the application of glue, steri-strips are applied, and the wound is covered with a dressing.

#### 7.1.1.4 Wound Site/Implant Site Assessment

#### 7.1.1.4.1 SURC Clinic (Initial 48 hours)

Wound Site/Implant Site Assessment will be carried out by the study PI [name] (trained in the evaluation by the study surgeon [name]), using the Implant Site Evaluation Form (ISEF). The wound/implant site will be assessed at  $24 \pm 2$  hours and 48 hours  $\pm 2$  hours after the procedure and more frequently if clinical indicated. Any concerns that are identified by the ISEF will be referred to the study surgeon for evaluation and treatment as per 7.6.2.

#### 7.1.1.4.2 Clinilabs Clinic (Post 48 hours)

Wound Site/Implant Site Assessment will be carried out by a research nurse (trained by the study surgeon [name]), using the ISEF as per the protocol time points outlined in Table 7-1. Any concerns that are identified by the ISEF will be initially referred to the Clinilabs doctor for evaluation and treatment as per 7.6.2. The Clinilabs doctor will consult with the study surgeon if required.

If there are any concerns to the wound/implant site by the participants outside of regular study visits, they will be asked to come to the Clinilabs clinic for evaluation as above. All evaluations will be documented using the ISEF.

Note: As appropriate, participants may be seen for follow-up visits at the SURC clinic (i.e. if clinically indicated or if traveling to the Clinilabs clinic presents a hardship to a participant).

#### 7.2 LABORATORY PROCEDURES/EVALUATIONS

#### 7.2.1 Clinical Laboratory Evaluations

Samples will be collected and sent for analysis to Lab Corp.

For the following test, 4.5 mL of blood will be collected in 1 tube (lavender top EDTA tube):

• [FBC] Full Blood Count: RBC, WBC, Hematocrit, Hemoglobin, Platelet Count, Eosinophils, Basophils, Monocytes, Neutrophils, Lymphocytes, Mean Corpuscular Volume (MCV), Mean Corpuscular Hemoglobin Concentration (MCHC), Mean Corpuscular Hemoglobin (MCH), Reticulocytes, Red cell distribution width (RDW), immature granulocytes

For the following tests, 5 mL of blood will be collected in 1 tube (red/grey mottled top gel barrier SST tube):

• [FCP] Full Chemistry Panel with Liver Function Tests: Glucose, Uric Acid, Blood Urea Nitrogen (BUN), Creatinine, Sodium, Potassium, Chloride, Calcium, Phosphorus, Protein Total, Albumin, Globulin, Albumin/Globulin A/G Ratio, Bilirubin (total), Bilirubin (direct), Bilirubin (indirect), Alkaline Phosphatase, Lactate Dehydrogenase (LDH), AST (SGOT), ALT (SGPT), GGT, Iron, Total Cholesterol, Triglycerides, HDL Cholesterol, LDL Cholesterol (calculated), Magnesium, CO2, CPK, Amylase, Lipase For the following tests, 5 mL of blood will be collected in 1 tube (lavender top EDTA tube):

- Hepatitis A IGG
- Hepatitis B Serology
- Hepatitis C Serology

For the following test, 5 mL of blood will be collected in 1 tube (red/grey mottled top gel barrier SST tube):

• *HIV Serology* 

For the following tests, a sample of urine is collected:

- UA (Urinalysis) including urine color, appearance, bilirubin, urobilinogen, WBC esterase and a microscopic examination (WBC, RBC, epithelial cells, mucus threads, bacteria)
- LEU (Leucocytes), NIT (Nitrite), PRO (Protein), pH, BLD (Blood), SG (Specific Gravity), KET (Ketones), GLU (Glucose)
- [UDS] Full drug screen including morphine, oxycodone, methadone, cocaine, amphetamines, hydromorphone, hydrocodone, codeine, methamphetamines, thc, benzodiazepines, fentanyl and buprenorphine assay.

**Pregnancy test**: For all female participants, a blood test is done initially, with urine tests done monthly afterwards. A blood test will be used to confirm a positive urine result.

#### 7.2.2 Other Assays or Procedures

#### 7.2.2.1 Naltrexone Blood Level Assay

9 mL of whole blood will be collected into 10cc Na Heparin (green top) tubes (see Section 7.2.4.1 for more details regarding the procedure).

#### 7.2.3 Total amount of Blood to be collected

The amount of blood drawn for the study is:

- HIV and Hepatitis screening = 10 mL.
- FCP and FBC = 180.5 mL (18 x 9.5 mL)
- Pregnancy testing (Female participants only) = 4 mL (during the trial, a blood test will be used to confirm a positive urine result)
- Total blood samples for naltrexone / naltrexol =  $288 \text{ mL} (32 \times 9 \text{ mL})$
- There is also the potential for further bloods to be taken on any un-scheduled visit for PK bloods (10 mL) and follow-up visit for outstanding AEs (FCP and FBC 9.5 mL) post end of trial.

**Note:** that the total blood samples for naltrexone / naltrexol have been calculated for the worst case of participants going out to Day 540. In the event that a participant registers two consecutive monthly naltrexone blood levels recorded at <0.1 ng/mL, then the participant will be withdrawn from the study and the blood collection will be reduced by 10 mL for every monthly time point not required.

#### 7.2.4 Specimen Preparation, Handling and Storage

#### 7.2.4.1 Naltrexone Blood Level Assay

All naltrexone blood samples will be collected in 1 x 10 mL Na Heparin tubes (9 mL) and stored in the refrigerator at 0-4°C until specimen preparation. Specimen preparation will be carried out within 30 minutes of collection. This will involve centrifugation of the blood sample in an ambient centrifuge for 15 min at 2,000 rpm within 30 minutes of collection to enable plasma separation. The plasma will be extracted and transferred into two 2 mL cryovials (2 aliquots total). Cryovials with aliquot will be stored in a freezer at no warmer than -70°C until shipment.

All plasma samples up to 48 hours will be collected, processed and stored at NYSPI. All plasma samples scheduled after 48 hours will be collected, processed and stored at Clinilabs. When batches of greater than 50 samples are available these can then be shipped on dry ice to the PK analysis laboratory for free (unconjugated) naltrexone and free (unconjugated)  $6-\beta$ -naltrexol analysis. Backup samples will remain stored at Clinilabs and NYSPI for the duration of the trial.

#### 7.2.5 Specimen Shipment

Plasma will be stored for batch shipment to the PK analysis laboratory for analysis. Storage of samples at no warmer than -70°C will be done at Clinilabs and NYSPI. Shipment of samples to the PK laboratory will be done under dry ice.

#### 7.3 STUDY SCHEDULE

#### 7.3.1 Screening Visit 1

Participant shall be screened for inclusion and exclusion criteria and overall suitability for the study.

- Obtain informed consent for screening.
- Review medical history to determine eligibility based on inclusion/exclusion criteria.
- Review medications history to determine eligibility based on inclusion/exclusion criteria.
- Perform medical and psychiatric examinations, including Patient Health Questionnaire (PHQ) and Beck Depression Inventory (BDI-II), MINI-International Neuropsychiatric Interview (MINI), needed to determine eligibility based on inclusion/exclusion criteria.
- Concomitant medication review.
- Physical (Record BMI) and mental status exam.
- Vital signs.
- A 12-lead ECG will be conducted for each measurement, the subject should be resting during the 10 minutes prior to the measurement time point and in a semi-recumbent or supine position at the measurement timepoint. RR, PR, QRS, QT, QTcF and QTcB will be collected. ECGs will be measured with equipment calibrated as per site standard operating procedures and will be assessed by a qualified clinician.
- C-SSRS-Lifetime.
- Breathalyzer Assessment

## 7.3.2 Screening Visit 2

Review of inclusion and exclusion criteria and overall suitability for the study.

- Collect blood for FBC, FCP.
- Collect urine for UA, and UDS.
- Collect blood for Hepatitis and HIV tests.
- Collect blood for baseline naltrexone and 6-β-naltrexol measurement.
- Collect blood for pregnancy test in female participants.
- Self-reported substance use (using the Recent Drug Use-Baseline [RDU]).
- Concomitant medication review.
- AE Monitoring.

## 7.3.3 Recruitment Visit

At the Recruitment visit the following will take place;

- Review of screening assessments and study inclusion exclusion criteria. All screening assessments must be collected within 30 days prior to the Recruitment visit,
- Obtain informed consent for IP administration.
- Concomitant medication review.
- AE Monitoring.
- Breathalyzer Assessment

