#### 5.2 PARTICIPANT EXCLUSION CRITERIA

An individual who meets any of the following criteria will be excluded from participation in this study:

- 1. Positive UDS at screening for illicit substances.
- 2. Is currently on naltrexone medication.
- 3. Has had a naltrexone implant in the past 24 months.
- 4. Has received treatment with an extended naltrexone product (e.g. Vivitrol) in the past 12 months.
- 5. Has a condition which requires treatment with opioid based medication.
- 6. Has a known hypersensitivity to naltrexone.
- 7. Has a known hypersensitivity to poly-lactic based materials e.g. biodegradable sutures, surgical implants or previous biodegradable implants.
- 8. Has a known hypersensitivity to local anesthesia.
- 9. Is prone to skin rashes, irritation or has a skin condition such as recurrent eczema that is likely to impact the implant site area, or as determined by the evaluating physician.
- 10. Demonstrates any abnormal skin tissue in the proposed implantation area.

- 11. Is pregnant or planning to be. Women need to have negative blood pregnancy test at screening. Women need to agree to practice dual contraceptives.
- 12. Participant is breastfeeding or planning to be.
- 13. Has a current significant neurological (including cognitive and psychiatric disorders), hepatic, renal, endocrine, cardiovascular, gastrointestinal, pulmonary, hematological or metabolic disease unless currently controlled and stable with protocol-allowed medication 30 days prior to proposed investigational product administration.
- 14. Any clinically important abnormal finding as determined by medical history, physical examination, ECG or clinical laboratory tests.
- 15. Any additional condition(s) that in the investigator's opinion would prohibit the participant from completing the study or would not be in the best interest of the participant.
- 16. ALT or AST > 3 times the upper end of the laboratory normal range.
- 17. Any methadone use 14 days prior to screening, and up to Study Day 0.
- Current DSM 5 diagnosis of schizophrenia, bipolar, anxiety, or depressive disorder, confirmed by MINI assessment, or currently treated with medications for anxiety or depression. Past history (in remission DSM 5 classification) of anxiety or depression is not exclusionary.
- 19. Any elevated risk for suicide measured using the Columbia Suicide Severity Rating Scale, endorsing any of the items in the past month (C-SSRS, Lifetime)

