- **Option 2:** Removal of the study medication via surgical procedure. Whilst removal of the study medication is straightforward in the early stages (up to about 10 days), removal after this becomes more complex as the OLANI biodegrades. Later procedures require a general anesthetic (with access to OR facilities) and may result in a large scar certainly larger than not removing the implant but the extent depends on the amount of tissue to be excised. The risks associated with general anesthetic vary between people, but about 20% of those receiving general anesthesia have minor AEs and 0.2% have major AEs including death. If removal of the implant is the only acceptable option to the participant, this will be arranged through either Columbia University Medical Center or another local hospital.

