#### 7.3.4 Day -1 to Day 2 ('Admission' Days)

#### 7.3.4.1 Admission Day -1

Participants will be admitted to the SURC clinic at the NYSPI where they will complete the PHQ, BDI-II, Substance Use assessment, urine drug screen, concomitant medication review and AE monitoring. Each participant will then undergo the NCT to confirm opiate naivety based on COWS score.

#### 7.3.4.2 Admission Day 0

Participants will be scheduled for administration of the OLANI as outlined in section 7.1.1.3. After a review of concomitant medications and vital signs are obtained, participants will be fitted with the iv cannula to aid in the collection of blood sample for the first 48 hours. There shall be no use of heparin to keep the cannula clear as this may affect the blood analysis of naltrexone and 6- $\beta$ -naltrexol. Processing and storage of blood samples shall be done as per section 7.2.4.1.

The recorded dose time (0 hour) will be the time at which the procedure will be completed. Naltrexone blood samples (see section 7.2.4.1) will be collected at the following time points: 3 hours  $\pm 60$  min, 6 hours  $\pm 60$  min, and 12 hours  $\pm 60$  min. The actual time of each PK sample collection shall be recorded.

Participants will also be monitored for AEs.

## 7.3.4.3 Admission Day 1

Naltrexone blood samples (see section 7.2.4.1) will be collected at 24 hours  $\pm 2$  hours after the OLANI procedure. The actual time of each PK sample collection shall be recorded.

Participants will also be monitored for AEs, have a review of concomitant medications and have a Wound Site/ Implant Site Assessment as per 7.1.1.4.

At this time, participants will have the option of remaining an inpatient or being discharged from the SURC clinic and returning for the 48-hour observation (Admission Day 2).

## 7.3.4.4 Admission Day 2

Naltrexone blood samples (see section 7.2.4.1) will be collected at 48hours  $\pm 2$  hours after the OLANI procedure. The actual time of each PK sample collection shall be recorded.

Participants will also be monitored for AEs, have a review of concomitant medications and have a Wound Site/ Implant Site Assessment as per 7.1.1.4.

Remaining inpatient participants will be discharged from the SURC clinic.

All participants will be provided with a timetable for their follow-up visits, which will be carried out at the Clinilabs clinic.

## 7.3.5 Follow-Up Day 4 to 540

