#### A PILOT PHARMACOKINETIC TRIAL OF THE O'NEIL LONG ACTING NALTREXONE IMPLANT CONFIDENTIAL Go-Medical Protocol GM0017: (Ver. 0.13; 11 June 2020)

	Screening Visit 1 	Screening Visit 2 	Recruitment Visit 	Admission Day -1 	Admission Day 0 	Admission Day 1 & 2 	Day 4  (±1 day)	Day 8  (±2 days)	Day 14, 21, 35, 42 & 49  (±3 days)	Day 28 & 56  (±3 days)	Monthly PK Visit  (±10 days)	Final Visit 	Early Termination / Withdrawal 	Un- scheduled Visit 	PK Follow- up 	AE Follow- up 
AE Monitoring		X	X	Х	X	х	X	X	Х	X	Х	X	Х	Х	X	X
Urine Drug Screen		X		Х						Х	Х	Х			Х	
Recent Drug Use- Baseline (RDU)		X														
Quantitative Substance Use Inventory	2 2			X						X	X	X		Х	X	
Naloxone Challenge Test			24  0	Х	2		2 2								S	- (s 2-
COWS Baseline, 10 Minutes, 20 Minutes, 30 Minutes				х				~ ~ ~ ~ ~ ~ ~ ~ ~ ~ ~ ~ ~ ~ ~ ~ ~ ~ ~								
Subcutaneous Implant (Dosing) EX	2°				Х								6. 10		2. 3	
Vital Signs (Height, Weight, BMI)	Х	1											83	28 N		
Vital Signs with weight 					Х		Х	X	Х	Х	X	Х	Х	Х	Х	Х
Wound Site/ Implant Site Assessment						X6	X	X	X	x	x	X	x	х	x	

1. Inclusion/exclusion criteria will only be reviewed at Screening Visit 2 and the Recruitment Visit.

2. C-SSRS will be used to assess suicidal risk. Lifetime risk will be assessed at screening visit 1, with subsequent visits assessing risk since last visit (SLV).

3. A blood sample will be taken for NTX & 6BN at Screening Visit 2.

4. Pregnancy testing will be conducted on all females of child bearing potential on serum at screening, subsequent testing will be carried out on urine samples with serum testing used to confirm positive urine results as per section 7.2.1.

5. Initial 48 hours PK Sampling - Blood samples will be collected at the following time points: Baseline screening visit, 3 hour ±60 min, 6 hour ±60 min, 12 hour ±60 min, 24 hour ±2 hours and 48 hour ±2 hours after the implant procedure. The actual time of each PK sample collection should be recorded.

6. Wound site/implant site assessment for day 1 (24h) and day 2 (48) will take place within ±2hours.

7. Monthly PK visit - Blood samples will be collected at the following time points: Day 90, 120, 150, 180, 210, 240, 270, 300, 330, 360, 390, 420, 450, 480, 510 & 540.

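### The only scheduled pregnancy test before implantation can be more than 30 days old on Day 0, and the next (Day 28 ±3) comes after the period in which the protocol calls removal straightforward

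*Combined protocol and SAP*

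**What the plan says.** Exclusion 11 in section 5.2 bars women who are pregnant or plan to be, asks for agreement to dual contraception, and adds: "Women need to have negative blood pregnancy test at screening". The draw is listed under Screening Visit 2 in section 7.3.2 ("Collect blood for pregnancy test in female participants"). Table 7-1 note 4 agrees: "Pregnancy testing will be conducted on all females of child bearing potential on serum at screening".

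Section 7.3.3 sets the age limit: "All screening assessments must be collected within 30 days prior to the Recruitment visit". Section 7.1.1.1 has the hospital stay for implantation arranged after enrolment and gives no deadline. Table 7-1 note 1 says: "Inclusion/exclusion criteria will only be reviewed at Screening Visit 2 and the Recruitment Visit".

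On Admission Day -1 participants are admitted to the clinic, "where they will complete the PHQ, BDI-II, Substance Use assessment, urine drug screen, concomitant medication review and AE monitoring", and then have the naloxone challenge (7.3.4.1). Before implantation on Day 0 the list is medication review, vital signs and a cannula (7.3.4.2). Neither list contains a pregnancy test.

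After implantation, section 7.2.1 describes the scheme as "a blood test is done initially, with urine tests done monthly afterwards". Section 7.3.5 and Table 7-1 place the first urine test at Day 28, with a ±3 day window.

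On removal, section 5.4.2.1 says "removal of the study medication is straightforward in the early stages (up to about 10 days" and that it is more complex after that, with a general anesthetic. The same section and 8.4.3 offer removal when a pregnancy is found.

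**The concern.** The pregnancy exclusion is meant to hold at implantation, but the evidence for it is tied to an earlier visit. A woman who conceives after Screening Visit 2, or who was tested too early to be positive, can be implanted with no protocol deviation. She would receive a product with a 540-day duration of therapy (6.1.9), in a study that section 2.3.2 says offers her cohort no known benefit.

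The timing of detection also matters on the protocol's own terms. Its text separates an early period in which removal is simple from a later one in which it is not, and the first scheduled test after implantation falls in the later one. The plan already re-checks other items on Day -1, including drug use by urine screen, so the omission is not explained by a general decision against late re-checking.

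**Working it through.** The plan gives no figure to reproduce, so the check is a reading of the schedule plus day counts.

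**Inputs**
- Maximum age of the screening test at Recruitment: 30 days (7.3.3).
- Interval from Recruitment to Day 0, called *g*: no limit in the available text. It is at least 1 day, because Day -1 precedes Day 0. Larger values below are assumptions for illustration.
- Next scheduled pregnancy test: Day 28 ±3, so Day 25 to Day 31 (7.3.5, Table 7-1).
- End of the period in which removal is called straightforward: about Day 10 (5.4.2.1).

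**Step 1. Is there a scheduled test between Screening Visit 2 and Day 28?** The lists for Recruitment (7.3.3), Day -1 and Day 0 (7.3.4), and Days 1 and 2 (7.3.4) contain none. The assessments that section 7.3.5 requires at every follow-up visit do not include one either, so Days 4, 8, 14 and 21 have none. The answer is no.

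**Step 2. Age of the negative result at implantation** = 30 + *g*.

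**Step 3. Longest interval between consecutive scheduled tests** = 30 + *g* + 28, ±3.

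| *g* (days, assumed) | Test age on Day 0 | Interval to nominal Day 28 |
|---|---|---|
| 1 | 31 | 59 |
| 7 | 37 | 65 |
| 14 | 44 | 72 |
| 30 | 60 | 88 |
| 60 | 90 | 118 |

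**Step 4. Delay of the first scheduled test past about Day 10**
- Day 25: 25 − 10 = 15 days
- Day 28: 28 − 10 = 18 days
- Day 31: 31 − 10 = 21 days

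Even the earliest visit inside the window misses the early-removal period.

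**Step 5. With a Day -1 test added**, the result is 1 day old at implantation, and the interval to the next scheduled test is 1 + 28 = 29 days (±3).

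**The case against.** The strongest reply is that the plan does not rely on one blood test. Exclusion 11 bars pregnancy itself, not just a positive result, and requires dual contraception. Section 5.4.1 allows withdrawal for an exclusion that is newly developed or was not recognized before. Adverse events are monitored at Recruitment, on Day -1 and Day 0, and on Days 4, 8, 14 and 21. Table 7-1 marks a pregnancy test as possible at an unscheduled visit. A suspected pregnancy could therefore be tested and found inside the first 10 days.

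All of this stands, and it lowers the risk. None of it schedules detection. Contraception does not reveal a pregnancy, withdrawal needs a known one, and note 15 leaves the unscheduled test to a physician's discretion.

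Four stronger readings are tempting, and the documents do not support them:
- *Pregnancy cannot be found before Day 28.* The scheduled test can fall on Day 25, and a discretionary test can come earlier.
- *The age of the test is unlimited.* The available text states no limit, but the study schematic is not part of it. The estimated study duration of 22 months against 540 days per participant leaves roughly 129 days (22 × 30.4 − 540) to screen and implant everyone. That is an estimate and not a rule, but it makes very long gaps unlikely.
- *A probability can be put on implanting a pregnant woman.* The documents give no conception rate and no distribution of gaps. Any figure would rest on assumed values of both, applied to up to 10 women.
- *The primary endpoint is at risk.* PK draws do stop on pregnancy (5.4.2.1), but section 5.3.1 already allows for 10 of 20 participants not completing. The loss of one profile is minor by comparison.

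A reader might also take the severity of late removal as settled. The protocol is not consistent on this. The pregnancy text in 5.4.2.1 and 8.4.3 describes the risks of anesthesia and of removal as minimal. Option 2 in 5.4.2.1 describes later removal as complex, with about 20% minor and 0.2% major adverse events for general anesthesia.

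**Conclusion.** The point holds as a gap in detection. A fully compliant site can implant on a negative pregnancy result at least 31 days old, and older by however long Recruitment to Day 0 takes. The next scheduled test comes 15 to 21 days after the protocol's own early-removal period ends.

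The first figure assumes that the screening test was taken at the limit of its 30-day window, and that no limit from Recruitment to Day 0 appears in the schematic. The second depends only on the stated visit window and the stated period of about 10 days.

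The event is possible rather than likely, and its probability cannot be estimated from the documents. The consequence for an individual participant, set against the very low cost of a test, makes this a should-fix.

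**What to change.** 1. Add a urine pregnancy test for women of childbearing potential to the Admission Day -1 list in 7.3.4.1 and to the Day -1 column of Table 7-1, using the urine already collected for the drug screen. The existing exclusion 11 is then checked on a current result, and no new eligibility rule is needed. Serum confirmation of a positive result is already provided for in 7.2.1.
2. In 7.3.3, count the 30-day window back from Day 0 instead of from the Recruitment visit, and repeat any screening assessment that has expired.
3. Add Day -1 to the eligibility review in Table 7-1 note 1.
4. Reconcile the statements on the risk of anesthesia and removal in the pregnancy text of 5.4.2.1 and in 8.4.3 with Option 2 of 5.4.2.1. Which account is right is for the sponsor and investigator to settle.

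The cost is about 10 dipsticks, an occasional repeat of screening tests when scheduling slips, and a short amendment. One limit remains: a very early pregnancy can be negative on Day -1 as well, and the next scheduled test would still be Day 28. Section 7.3.5 shows that follow-up was under way by April 2020. If implantation is already complete, the change applies to any additional participants that 7.3.8 foresees and to the follow-on study mentioned in 2.2.
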